# Safety and This study will assess the safety and tolerability of the chosen doses of ISLA101 **Tolerability** (fenretinide oral capsules) as assessed by AEs, TEAEs, vital signs, physical **Evaluation** examinations, and clinical laboratory tests. As clinical studies from IND38892 and from the published literature showed ocular toxicity upon treatment with fenretinide (eye irritation, dryness of eyes, nyctalopia), an ophthalmologist will be available to evaluate all significant ocular complaints. Discontinuation from the study will be at the discretion of the ophthalmologist. Due to teratogenic risks, all initial reports of pregnancy in female subjects or partners of male subjects must be reported to the Sponsor by the site personnel within 72 hours of their knowledge of the event. The safety and tolerability data will be reviewed by an independent SRC before proceeding to the next dose cohort. **Dose-limiting Adverse** The incidence and nature of any AEs, dose-limiting AE, SAEs, vital sign changes, **Events** ECG changes, and laboratory abnormalities will be assessed on an ongoing basis by the Investigator. Dose-limiting AEs are defined as clinically significant AEs or abnormal laboratory values that are Grade 3 or 4, based on toxicity grading scales as specified in FDA's Guidance for Industry and Investigators – Toxicity Grading Scale for Healthy Adult and Adolescent Volunteers Enrolled in Preventive Vaccine Clinical Trials. The following signs of drug toxicity will be deemed to be of special interest: • sustained respiratory depression that results in oxygen saturation below 92% seizure • protracted nausea and vomiting • any AE deemed by the Investigator to be dose-limiting or Grade 3 and above • signs of drug-induced liver injury based on the following criteria from FDA guidance (Drug-Induced Liver Injury: Premarketing Clinical Evaluation): ALT or AST $> 8 \times ULN$ • ALT or AST > 3 x ULN and (total bilirubin > 2 x ULN or international normalized ratio > 1.5) • ALT or AST > 3 x ULN with the appearance of fatigue, nausea, vomiting, right upper quadrant pain or tenderness, fever, rash, and/or eosinophilia (> 5%) Escalation from one dose level to the next will occur following the safety review by the SRC. If blinded study drug demonstrates an acceptable safety profile in the previous cohort, enrollment of the next higher dose cohort may begin. In the case of dose-limiting AE, dose reduction or repeat of the cohort with the previously tested dose may occur. **Dose Escalation** The decision to enroll the sequential cohort at the next dose level will be based on Criteria the safety data from previous dose cohorts. Dose escalation will depend on the emergence of dose-limiting AEs and review of the safety data. Progression to the next higher dose will only occur if the previous dose level was deemed to be safe and well tolerated by the SRC. Safety data sets to be reviewed by the SRC for dose escalation determination will include all available data up to 96 hours post-dosing for subjects enrolled into each dose-level cohort. A minimum of 7 subjects' data will be evaluated to make dose escalation decisions.

	Doses will be flexible during the study to allow for reductions in the planned escalation based on safety. When it is not appropriate to escalate the dose, then a previous dose, or an intermediate dose may be given following discussion between the Investigator and Sponsor.
Stopping Criteria for the Study	Further enrollment and study drug administration will be stopped if any of the following events occur:
	
 
A single SAE regardless of organ system if it is possibly, probably, or definitely related to the study drug;
 

	
 
Grade 3 or higher AEs and laboratory abnormalities determined to be possibly, probably, or definitely related to study drug should result in prompt discontinuation of study treatment;
 

	
 
Death of any subject considered related to study drug unless the SRC determines it is unrelated to study drug;
 

	
 
An anaphylactic reaction to study drug in any subject;
 

	
 
A potentially life-threatening AE or SAE, unless the SRC determines it is unrelated to study drug;
 

	• A pattern of significant symptoms, physical findings, or laboratory abnormalities that, although individually minor, collectively may represent a safety concern in the opinion of the Investigator or the medical monitor and are judged by the SRC to be at least possibly related to study drug; or
	• Sponsor's decision to terminate the study for any reason.
	The human research ethics committee (HREC),), the FDA and local regulatory agencies as required will be notified if the study hold criteria are met.
Pharmacokinetic Evaluation	Blood samples will be collected at the pre-determined time points pre- and post-dosing to characterize the PK profile of plasma fenretinide and its metabolites N-(4-methoxyphenyl) retinamide (MPR) and 4-oxo-N-(4-hydroxyphenyl) retinamide (oxo-HPR) and to capture appropriate PK parameters. PK samples will be analyzed and evaluated after completion of all cohorts. The PK sampling time points will be: pre-dose and 0.5, 0.75, 1, 1.5, 2, 3, 4, 5, 6, 8, 10, 12,24, 36, 48, 72 and 96 hours post-dose.
Statistical Methods	A statistical analysis plan (SAP) describing all statistical analyses will be provided as a separate document prior to data base lock.
	Sample Size Considerations: The study is considered to be exploratory with a sample size of 8 subjects per cohort (2 placebo + 6 active); this is considered sufficient to evaluate the safety profile and provide sufficient PK information for future development of the compound.  General Statistical Methodology: Demographic data will be summarized using descriptive statistics. Descriptive statistics will be used to provide an overview of the safety results. For categorical
	parameters, the number and percentage of subjects will be presented. For continuous parameters, descriptive statistics will include n (number of subjects), mean, standard deviation, median, minimum, and maximum. No imputations will be made for missing data.

# **Analysis Populations**

Two analysis populations will be used to summarize the results from this study:

- Safety Population: All subjects who receive at least 1 dose of study drug.
- PK Population: All subjects in the safety population who have a pre-dose PK sample, and at least 1 post-dose analyzable PK sample.

Subjects disposition will be summarized and will include all subjects who have received one dose of study drug in the safety population, subjects in the PK population, and number and percent of subjects who complete or prematurely discontinue the study, along with reason for discontinuation. Baseline demographic data will be summarized for all subjects who were randomized in this study and took at least 1 dose of study drug.

#### Safety Analysis

Safety will be assessed by the evaluation of AEs, TEAEs, laboratory test results, vital sign measurements, physical examination findings, and tolerability assessment. Safety variables will be tabulated and presented for all subjects in the Safety Population by dose. The AEs will be summarized and presented by dose and visit and overall. Change from screening in clinical laboratory parameters and vital sign parameters will be summarized by visit and overall. Shifts from baseline in continuous laboratory assessments will be tabulated.

#### PK Analyses

Pharmacokinetic and statistical analysis will be done using validated software (eg, Phoenix® WinNonlin® version 8.0 or higher).

Pharmacokinetic parameters will be derived following noncompartmental analysis based on concentration-time data for fenretinide and its metabolites N-(4-methoxyphenyl)retinamide (MPR) and 4-oxo-N-(4-

hydroxyphenyl)retinamide (oxo-HPR). On the day of dosing, the following parameters will be derived:  $C_{max}$ ,  $AUC_{last}$ ,  $AUC_{inf}$ ,  $T_{max}$ ,  $T_{\frac{1}{2}}$ , Cl/F, and V/F. Other parameters will be estimated as applicable.

Dose proportionality for key exposure parameters for fenretinide ( $C_{max}$ ,  $AUC_{last}$ , and  $AUC_{inf}$ ) will be calculated based on the dose-normalized parameters. Descriptive statistics (n, mean, SD, geometric mean, %CV, median, minimum, and maximum) will be used to summarize the calculated PK parameters by dose level. For  $T_{max}$  and  $T_{1/2}$ , only n, median, minimum, and maximum will be presented.

Analyses of variance (ANOVA) will be performed on ln-transformed PK parameters  $AUC_{last},\,AUC_{inf},\,$  and  $C_{max}$  to evaluate fenretinide food effect for the recalled cohort. The ANOVA will include a calculation of least-squares means (LSMs), the differences between adjusted means, and the standard error associated with these differences. Ratios of means will be calculated using the LSM for ln-transformed  $AUC_{last},\,AUC_{inf},\,$  and  $C_{max}.\,$  The 90% confidence interval (CI) for the difference between fed and fasted conditions will be calculated for the parameters  $AUC_{last},\,AUC_{inf},\,$  and  $C_{max}$  using ln-transformed concentration data. The CIs will be expressed as a percentage relative to the LSM.

# SCHEDULE OF ASSESSMENTS

Table 1

Study Procedures and Assessments to Dose Under Fasted (Cohorts 1-3) and Fed Condition (Cohort 4)

				Cohorts 1-3	s 1-3							Cohort 4	4		
	Study Period	Screening	Clinic Check- in	Tra	eatme	Treatment Period	iod	Follow- up/ET	Clinic Check- in	·	Treatment Period	nent P	eriod		Follow- up/ET
Study Procedure	Study Day	-28 to -2	-1	1	2 3	3 4	5	8	66	10	11	12	13	14	17
	Visit Window (days)	N/A		eduI	Inpatient			+/-1	£-/+		Ir	Inpatient	t.		+/-1
Informed Consent		X							X						
Inclusion/Exclusion Criteria		X	X						X						
Demographics		X													
Height and weight		X							X						
Medical History		X	X						X						
Vital Signs 		X	X	X	X	X	X	X	X	X	X	X	X	X	X
12-lead		;	;	;					;	;					
electrocardiogram (ECG) 		×	×	×					×	×					
Full Physical Exam		X	X					X	X						X
Hep B, Hep C, HIV		X													
Safety laboratory tests															
(chemistry,		X	×	×	×	×	×	×	×	×	×	×	×	×	×
coagulation, urinalysis)															
Pregnancy test 		X	X					X	X						X
FSH 		X													
Urine screen for drugs of abuse 		X							X						
Alcohol breath test		X	X						X						
Admission			X	$\exists$	$\dashv$				X						

Study drug administration			×						X 6					
High-fat, high-calorie breakfast									X					
PK blood samples 			X		X	X			X	X	X	X	X	
Adverse events 	X	X	X	X	X		X	X	X	X	X	X	X	X
Concomitant medication review	X	X	X	X	X	X	X	X	X	X	X	X	X	X
Discharge						X							X	

ECG = electrocardiogram; ET = early termination; FSH = follicle-stimulating hormone; Hep = hepatitis; HIV = human immunodeficiency virus; PK = pharmacokinetic(s);

Vital signs include blood pressure, pulse, respiration and temperature.

12-lead ECG will be performed in triplicate at screening, and on Day -1 (check-in) to confirm eligibility, and on Day 1 at 5 hours (±15-minute) post dose. A single ECG will be performed on Day 9 (check-in) and on Day 10 at 5 hours (±15-minute) post dose.

A serum pregnancy test will be performed at screening and urine pregnancy test will be performed at check-in and at follow-up for all female subjects.

4 For all female subjects to confirm or refute postmenopausal status.

A nicotine urine or breath test may be utilized for tobacco use testing at site discretion.

Study drug will be administered approximately 30 minutes after start of a high-fat, high-calorie meal; 100% meal consumption is preferred.

PK sampling to assess the PK of fenretinide will be performed at the time points as specified in Table 2.

Monitoring for serious adverse events begins when the informed consent form is signed; and treatment-emergent adverse events begins after the first dose is administered.

 Study day is relative to study drug administration for the subjects in Cohort 3.

Study Schedule and Sampling Time Points for Pharmacokinetic Analysis Table 2

	-1 0.5 0.75 1 1.5 2 3 4 5 6 8 10 12 24 36 48 72	+/-5 +/-15				X							
	Time Relative to Dose (hours) a $\begin{bmatrix} -1 & 0.5 & 0.75 \end{bmatrix}$	Assessment Window (minutes) b +/-2	1	2	3	4	5	10 X X X	11	12	13	14	
1				£-I	8 1 10		в П 1	ւ Տ ր ոդ		hor	Co		

a: Time from dose begins when first capsule is consumed

b: Vital signs should be assessed prior to PK samples taken

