## Statistical Analysis Plan

**Sponsor:** Island Pharmaceuticals Ltd  
**Protocol Number:** ISLA101-P01-CT001

Study Procedure		Cohorts 1-3						Cohort 4								
	Study Period	Screening	Clinic Check-in	Treatment Period				Follow-up/ET	Clinic Check-in	Treatment Period				Follow-up/ET		
	Study Day	-28 to -2	-1	1	2	3	4	5	8	9 	10	11	12	13	14	17
	Visit Window (days)	N/A	Inpatient				+/-1		+/-3	Inpatient				+/-1		
Study drug administration				X						X 						
High-fat, high-calorie breakfast										X						
PK blood samples 				X	X	X	X	X		X	X	X	X	X		
Adverse events 		X	X	X	X	X	X	X	X	X	X	X	X	X		
Concomitant medication review		X	X	X	X	X	X	X	X	X	X	X	X	X		
Discharge								X						X		

ECG = electrocardiogram; ET = early termination; FSH = follicle-stimulating hormone; Hep = hepatitis; HIV = human immunodeficiency virus; PK = pharmacokinetic(s);

 Vital signs include blood pressure, pulse, respiration and temperature.

 12-lead ECG will be performed in triplicate at screening, and on Day -1 (check-in) to confirm eligibility, and on Day 1 at 5 hours ( $\pm$ 15-minute) post dose. A single ECG will be performed on Day 9 (check-in) and on Day 10 at 5 hours ( $\pm$ 15-minute) post dose.

 A serum pregnancy test will be performed at screening and urine pregnancy test will be performed at check-in and at follow-up for all female subjects.

 For all female subjects to confirm or refute postmenopausal status.

 A nicotine urine or breath test may be utilized for tobacco use testing at site discretion.

 Study drug will be administered approximately 30 minutes after start of a high-fat, high-calorie meal; 100% meal consumption is preferred.

 PK sampling to assess the PK of fenretinide will be performed at the time points as specified in Table 2.

 Monitoring for serious adverse events begins when the informed consent form is signed; and treatment-emergent adverse events begins after the first dose is administered.

 Study day is relative to study drug administration for the subjects in Cohort 3.

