**Statistical Analysis Plan**

**Sponsor:** Island Pharmaceuticals Ltd  
**Protocol Number:** ISLA101-P01-CT001

The summary of ECG overall assessment table will present summaries for the baseline and each scheduled post-baseline visit for the overall result (Normal, Abnormal not clinically significant and Abnormal clinically significant).

If multiple tracings are conducted as part of one assessment, the mean of the three tracings per parameter and the worst clinical interpretation per timepoint will be summarized for each subject. All values will be listed including the mean value per parameter and the worst clinical interpretation. Changes from baseline will be calculated based on the mean values of the triplicates where appropriate.

The listings of ECG results will include all data (collected at scheduled and unscheduled visits) in the clinical database. The observations that were used as the baseline records for each parameter will be flagged and the change from baseline values at each post-baseline visit will be presented.

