Placebo Fasted (N=xx)														
Baseline[1]		xx	xx.xx	xx.xxxx	xx.xx	xx.x	xx.x	xx.x	-					
Day 1- 5 hours post dose		xx	xx.xx	xx.xxxx	xx.xx	xx.x	xx.x	xx.x	xx	xx.xx	xx.xxxx	xx.xx	xx.x	xx.x
Placebo Fed (N=xx)														
Baseline[1]		xx	xx.xx	xx.xxxx	xx.xx	xx.x	xx.x	xx.x	-					
Day 1- 5 hours post dose		xx	xx.xx	xx.xxxx	xx.xx	xx.x	xx.x	xx.x	xx	xx.xx	xx.xxxx	xx.xx	xx.x	xx.x

SD: Standard deviation, - : Not applicable.

[1] The baseline value is defined as the last available valid assessment collected prior to study drug administration in that period. Where triplicate measurements were taken, summaries were based on the mean of the triplicate measurements at each visit/time point.

Program Name: xxx.sas, Creation Date Time: YYYY-MM-DD HH:MM

Page 1 of x

**Tables, Listings and Figures Shells****Sponsor:** Island Pharmaceuticals, Ltd**Protocol Number:** ISLA101-P01-CT001

Sponsor: Island Pharmaceuticals Ltd  
 Protocol: ISLA101-P01-CT001

Table 14.3.6.2.1 Summary of 12-Lead ECG Overall Assessment (Safety Population)

Treatment Group Visit: Time Point	Overall Assessment			
	n	Normal n (%)	Abnormal NCS n (%)	Abnormal CS n (%)
ISLA101 300 mg Fasted (N=xx)				
Baseline[1]	xx	xx (xx.xx%)	xx (xx.xx%)	xx (xx.xx%)
Day 1- 5 hours post dose	xx	xx (xx.xx%)	xx (xx.xx%)	xx (xx.xx%)
ISLA101 600 mg Fasted (N=xx)				
Baseline[1]	xx	xx (xx.xx%)	xx (xx.xx%)	xx (xx.xx%)
Day 1- 5 hours post dose	xx	xx (xx.xx%)	xx (xx.xx%)	xx (xx.xx%)
ISLA101 900 mg Fasted (N=xx)				
Baseline[1]	xx	xx (xx.xx%)	xx (xx.xx%)	xx (xx.xx%)
Day 1- 5 hours post dose	xx	xx (xx.xx%)	xx (xx.xx%)	xx (xx.xx%)
Pooled Placebo (N=xx)				
Baseline[1]	xx	xx (xx.xx%)	xx (xx.xx%)	xx (xx.xx%)
Day 1- 5 hours post dose	xx	xx (xx.xx%)	xx (xx.xx%)	xx (xx.xx%)
...				

CS: Clinically Significant, NCS: Not Clinically Significant

[1] The baseline value is defined as the last available valid assessment collected prior to first study drug administration.

Percentage (%) are based on the number of participants (n) with assessments available at the relevant post-baseline visit.

Where triplicate measurements were taken, summaries were based on the worst overall interpretation of the triplicate measurements at each visit/time point.

Program Name: xxx.sas, Creation Date Time: YYYY-MM-DD HH:MM

Page 1 of x

Programmer note:

The treatment groups will be displayed for the following: ISLA101 300 mg Fasted, ISLA101 600 mg Fasted, ISLA101 900 mg Fasted, Pooled Placebo.

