**Tables, Listings and Figures Shells****Sponsor:** Island Pharmaceuticals, Ltd**Protocol Number:** ISLA101-P01-CT001

**Sponsor:** Island Pharmaceuticals Ltd  
**Protocol:** ISLA101-P01-CT001

Table 14.3.6.2.2 Summary of 12-Lead ECG Overall Assessment - Fasted and Fed Cohorts (Safety Population)

Treatment Group Visit: Time Point	n	Overall Assessment		
		Normal n (%)	Abnormal NCS n (%)	Abnormal CS n (%)
ISLA101 xxx mg Fasted (N=xx)				
Baseline[1]	xx	xx (xx.xx%)	xx (xx.xx%)	xx (xx.xx%)
Day 1- 5 hours post dose	xx	xx (xx.xx%)	xx (xx.xx%)	xx (xx.xx%)
ISLA101 xxx mg Fed (N=xx)				
Baseline[1]	xx	xx (xx.xx%)	xx (xx.xx%)	xx (xx.xx%)
Day 1- 5 hours post dose	xx	xx (xx.xx%)	xx (xx.xx%)	xx (xx.xx%)
Placebo Fasted (N=xx)				
Baseline[1]	xx	xx (xx.xx%)	xx (xx.xx%)	xx (xx.xx%)
Day 1- 5 hours post dose	xx	xx (xx.xx%)	xx (xx.xx%)	xx (xx.xx%)
Placebo Fed (N=xx)				
Baseline[1]	xx	xx (xx.xx%)	xx (xx.xx%)	xx (xx.xx%)
Day 1- 5 hours post dose	xx	xx (xx.xx%)	xx (xx.xx%)	xx (xx.xx%)
...				

CS: Clinically Significant, NCS: Not Clinically Significant

[1] The baseline value is defined as the last available valid assessment collected prior to first study drug administration.

Percentage (%) are based on the number of participants (n) with assessments available at the relevant post-baseline visit.

Where triplicate measurements were taken, summaries were based on the worst overall interpretation of the triplicate measurements at each visit/time point.

Program Name: xxx.sas, Creation Date Time: YYYY-MM-DD HH:MM

Page 1 of x

**Tables, Listings and Figures Shells****Sponsor:** Island Pharmaceuticals, Ltd**Protocol Number:** ISLA101-P01-CT001

**Sponsor:** Island Pharmaceuticals Ltd  
**Protocol:** ISLA101-P01-CT001

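### Table 14.3.6.2.2 sets the worst of three fasted ECG tracings beside a single fed tracing, which inflates the fasted abnormal rate and makes the fed period look cleaner

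*Protocol*

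**What the plan says.** **Number of tracings.** Protocol Table 1, footnote 2, says of the fasted period: "12-lead ECG will be performed in triplicate at screening, and on Day -1 (check-in) to confirm eligibility, and on Day 1 at 5 hours" post dose. For the fed period (Cohort 4) it says "A single ECG will be performed on Day 9 (check-in) and on Day 10", again at 5 hours. SAP Table 1 repeats this: "A single ECG will be performed on Day 9 (check-in) and on Day 10 at 5 hours". Protocol section 8.1 says that fed-period assessments generally repeat the fasted ones unless Table 1 differs. Neither Table 1 nor section 8.2.5 gives a reason for the difference.

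**Summary rule.** SAP section 6.8.5 sets two rules for multiple tracings: "the mean of the three tracings per parameter and the worst clinical interpretation per timepoint will be summarized for each subject". Numeric parameters use the mean; only the overall interpretation uses the worst.

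**Fasted/fed shells.** Table 14.3.6.2.2 (Normal, Abnormal NCS, Abnormal CS) carries the footnote "Where triplicate measurements were taken, summaries were based on the worst overall interpretation of the triplicate measurements at each visit/time point". Table 14.3.6.1.2 (heart rate and intervals) carries "Where triplicate measurements were taken, summaries were based on the mean of the triplicate measurements at each visit/time point". Neither says that fed rows are single readings.

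**Baseline.** Table 14.3.6.1.2 states: "The baseline value is defined as the last available valid assessment collected prior to study drug administration in that period". Table 14.3.6.2.2 instead ties baseline to the first administration of study drug, as does the general definition in SAP section 5.1.2.

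**The concern.** Cohort 4 brings back the subjects of the highest tolerated fasted cohort on the same treatment assignment, so the fasted/fed tables compare subjects with themselves. A reader will take a difference between the rows as a food effect or as chance. In Table 14.3.6.2.2 part of any difference comes from the measurement rule, because the worst of three readings is at least as bad as any one of them.

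The distortion favours the fed condition, in which exposure may differ from the fasted condition. A real increase in abnormal ECGs when fed could be offset by the inflated fasted count. The table could also suggest that food improves the ECG profile when nothing has changed.

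The baseline footnote can add to this. Read literally, the fed rows of Table 14.3.6.2.2 compare a worst-of-three Day -1 baseline with one Day 10 tracing. That would look like improvement after fed dosing.

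**Working it through.** The documents give no ECG abnormality rate and no sample size calculation, so there is no planned figure to reproduce.

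**Inputs from the documents:** three tracings per fasted timepoint and one per fed timepoint (Table 1, footnote 2); 6 active and 2 placebo subjects per cohort (protocol section 3.1).

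**Assumptions, not in the documents:** the probability p that one tracing is read abnormal, taken as 5, 10 and 20%; and the correlation ρ between readings in a triplicate, taken from 0 to 1.

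**Categorical table, no true food effect.** The fed probability of an abnormal classification is p. The fasted probability is as follows.

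- Independent tracings: 1 − (1 − p)³. At p = 0.10 this is 1 − 0.729 = 0.271.
- Correlated tracings (beta-binomial): with s = (1 − ρ)/ρ, a = ps and b = (1 − p)s, it is 1 − [b(b+1)(b+2)] / [(a+b)(a+b+1)(a+b+2)]. At p = 0.10 and ρ = 0.5, s = 1, giving 1 − (0.9 × 1.9 × 2.9)/(1 × 2 × 3) = 1 − 0.8265 = 0.1735.

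Fasted probability, with the fasted/fed ratio in brackets:

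| p (fed) | ρ = 0.8 | ρ = 0.5 | ρ = 0 |
|---|---|---|---|
| 0.05 | 0.0647 (1.29) | 0.0892 (1.78) | 0.1426 (2.85) |
| 0.10 | 0.1278 (1.28) | 0.1735 (1.73) | 0.2710 (2.71) |
| 0.20 | 0.2491 (1.25) | 0.3280 (1.64) | 0.4880 (2.44) |

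At ρ = 1 the ratio is 1.00.

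**In subjects.** With 6 active subjects and p = 0.10, the expected abnormal count when fed is 6 × 0.10 = 0.60. When fasted it is 0.77, 1.04 or 1.63 at ρ = 0.8, 0.5 or 0. The chance of at least one abnormal subject is 1 − 0.9⁶ = 47% fed, against 56%, 68% or 85% fasted.

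**Baseline read literally.** At p = 0.10 and ρ = 0.5, the fed rows would move from an expected 17.4% abnormal at baseline to 10% at Day 10 with no change in the subjects.

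**Numeric table.** A mean of three tracings has the same expectation as one, so group means are unbiased. The spread differs:

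- If tracing noise is a share f of single-tracing variance, the fasted/fed SD ratio is √(1 − f + f/3). For f = 10, 30 and 50% it is 0.97, 0.89 and 0.82.
- For change from a same-period baseline, counting tracing noise alone with SD s, the variance is 2s² fed and 2s²/3 fasted. The SD ratio is √3 = 1.73.
- With an assumed s of 8 ms and a mean largest-of-six normal deviate of 1.267, the expected largest change is 1.267 × 8 × √(2/3) = 8.3 ms fasted and 1.267 × 8 × √2 = 14.3 ms fed.

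Extremes in this table therefore lean toward the fed period.

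**With equal tracings.** If one tracing per timepoint is classified in both periods, both expectations are p and the ratio is 1.00.

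**The case against.** The strongest points on the other side are these.

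- **Tracings from one sitting are strongly correlated.** Persistent findings should recur in all three. At ρ = 0.8 and p = 10% the gap is 0.77 − 0.60 = 0.17 of a subject among 6. This stands as to size; the direction does not change.
- **Like-for-like comparisons exist.** The shells have separate placebo fed rows, so active fed against placebo fed is single against single. That is true, but with 2 placebo subjects it cannot reveal or correct the imbalance.
- **All tracings are listed.** Listings 16.2.9.2.1 and 16.2.9.2.2 show each trace. This makes the first tracing recoverable, but a listing does not correct a summary table.
- **Little hangs on it.** The fed objective is PK only, SAP section 6.8 plans no formal safety comparisons, and a clinically relevant diagnostic finding is an AE under protocol section 9.1.1 whatever the table shows. This stands and sets the severity.

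A reader might infer more than the documents support:

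- **That both fasted/fed ECG tables are biased toward abnormal fasted readings.** The worst-of-tracings rule does not reach Table 14.3.6.1.2, which uses means.
- **That the 2.4 to 2.9 ratio is the expected size.** It requires independent tracings and is the upper end of the range.
- **That displayed SDs of change will be 1.73 times larger when fed.** That figure covers tracing noise only. Real variation between occasions is not reduced by averaging tracings, so the displayed ratio would be smaller.
- **That the fed schedule must become triplicate.** Protocol and SAP agree on single fed tracings, and the bias can be removed in the analysis without an added procedure.

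**Conclusion.** The point holds for Table 14.3.6.2.2. Its fasted and fed rows rest on different numbers of tracings under a worst-reading rule, which raises the fasted abnormal rate unless the tracings always agree. Over assumed per-tracing rates of 5 to 20%, the inflation runs from about 1.25-fold at high correlation to 2.9-fold at independence. The direction follows from the documents; the size rests entirely on the assumed p and ρ.

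The distortion lies in the fasted-against-fed comparison. Within the fasted period, baseline and Day 1 are both worst-of-three, so Table 14.3.6.2.1 is internally consistent. Table 14.3.6.1.2 has unbiased averages but a spread and extremes that should not be compared between periods. The two shells' baseline footnotes also conflict.

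Severity is low. The table could mislead a reader about food and ECG findings, but ECG is not a listed primary endpoint and the safety analysis is descriptive.

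**What to change.** Before database lock:

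1. In SAP section 6.8.5 and the footnote of Table 14.3.6.2.2, state that this table classifies each fasted timepoint by the first tracing of the triplicate, to match the single fed tracing. Keep worst-of-three in Table 14.3.6.2.1 and all tracings in the listings.
2. Keep the triplicate mean in Table 14.3.6.1.2 and add a footnote that fed values are single readings, so SD, minimum and maximum are not comparable between periods. Replacing the fasted mean by one tracing would lose precision with no gain in bias.
3. Give Table 14.3.6.2.2 the same within-period baseline as Table 14.3.6.1.2, so that the fed rows use Day 9.

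The cost is a few sentences of SAP and shell text, with no change to the schedule. The downside is that the same subjects' fasted category may differ between Tables 14.3.6.2.1 and 14.3.6.2.2, which the new footnote should say. The first-tracing rule also assumes that the order of tracings within a triplicate does not affect the reading.
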